### 7.2.6 Rate of AML Transformation, Transition to HSCT, and Transfusion Independence

Rate of AML transformation, transition rate to HSCT, and rate of RBC TI and/or platelet TI will be analyzed using the similar methodology as CR rate.

### 7.3 Pharmacokinetics

Whole blood concentrations of APR-548 will be measured in the safety run-in period and in Cycle 1 of the combination portion, at the timepoints provided in [Table 13](#). Plasma samples from Cycle 1 for analysis of azacitidine will be taken as indicated in [Table 13](#).

**Table 13. PK blood sampling timepoints for APR-548 and azacitidine in the safety run-in period and subsequent cycles**

Period	Day	Time relative to APR-548 dose (h)									
		Pre-dose	0.25 a	0.5 a	0.75 a	1 b	1.5 b	2 b	4 b	6 b	8 b
Safety Run-In (APR-548 monotherapy)	1	×	×	×	×	×	×	×	×	×	×
	2	×									
	4	×	×	×	×	×	×	×	×	×	×
	5	×									
Cycle 1 (APR-548 + Azacitidine)	1	×	×	×	×	× c,d	×	× d	× d	× d	× d
	2	× d									
	4	×	×	×	×	× c,d	×	× d	× d	× d	× d
	5	× d									
Subsequent cycles	1	×				×		×			

- a. A window of  $\pm 5$  minutes is allowable for this collection.
- b. A window of  $\pm 15$  minutes is allowable for this collection.
- c. Cycle 1 of combination therapy. Whole blood sample for APR-548 analysis and plasma sample for azacitidine analysis directly prior to azacitidine administration.
- d. Cycle 1 of combination therapy. Plasma samples for azacitidine administration to be taken at the same time as whole blood samples for APR-548.

The PK sampling timepoints (0.25, 0.75, 1.5 hours post dose) can be reduced once the  $C_{max}$  and  $T_{1/2}$  are established. The Sponsor will provide a written memo to sites, which should be submitted to IRBs and can be implemented per local site requirements.

PK blood sample for the measurements of whole blood concentrations of the unstable MQ adducts MQ-H2O, MQ-Cys and MQ-GSH will be implemented at selected centers which are equipped to conduct the critical sampling handling procedures described in the lab manual. All subjects enrolled in these centers will participate in this assessment and it is anticipated that data from at least 6 subjects will be available. The PK sampling schedule is provided in [Table 14](#).

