Azacitidine is rapidly absorbed after s.c. or i.v. administration with a  $V_d$  of  $76 \pm 26$  L and a  $T_{1/2}$  of  $41 \pm 8$  minutes.  $C_{max}$  is reached after about 30 minutes. Azacitidine and its metabolites are known to be substantially excreted by the kidney, and the risk of adverse reactions to this drug may be greater in patients with impaired renal function. Urinary excretion is the primary route of elimination; the cumulated urinary excretion is 85% of radioactive dose with less than 1% recovered in feces over 3 days.

Azacitidine undergoes spontaneous hydrolysis in aqueous solution and is deaminated by cytidine deaminases. Preliminary data indicate that drug-drug interaction with APR-548 as perpetrator are not likely, but the drug-drug interaction will be investigated as part of the current trial.

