## 4.3 Drug Products

### 4.3.1 APR-548

### 4.3.2 Azacitidine

*Chemical Name:* 4-amino-1- $\beta$ -D-ribofuranosyl-s-triazin-2(1H)-one.

*Formulation, preparation, storage and stability:* Please see commercial package insert approved by regulatory agencies.

*Route of Administration:* s.c. injection or i.v. infusion administered s.c. or i.v. for 7 consecutive days (Days 1-7). S.c. route is preferred but will allow for i.v. at the investigator's discretion.

However, the same route should be maintained over the 7-day treatment period (whichever route of administration is used on Day 1, the same route should be followed on all other days). On the days of concomitant APR-548 administration, azacitidine will be administered 1 hour ( $\pm 15$  min) after APR-548 intake. Missed doses, such as for a weekend or holiday, for any reason but toxicity may, at the investigator's decision, be replaced by adding an additional dosing day for azacitidine so that the subject receives the total 7 days of treatment per cycle. If the azacitidine dose interruption is  $>3$  days, discuss with the Medical Monitor.

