### 5.1.2 Azacitidine

Azacitidine is given at the standard dose of 75 mg/m^2 s.c. or i.v. over 7 consecutive days, Days 1 – 7. Cycles should be repeated every 28 days. S.c. route is preferred but i.v. is allowed at the investigator's discretion. The same route should be maintained over the 7-day treatment period (whichever route of administration is used on Day 1; the same route should be followed on all other days). On days of concomitant APR-548 intake, azacitidine should be administered 1 hour ( $\pm$ 15 min) after APR-548. Detailed instructions on preparation and administration can be found in the current United States Prescribing Information (USPI). Missed doses, such as for a weekend or holiday, for any reason but toxicity may, at the investigator's decision, be replaced by adding an additional dosing day for azacitidine so that the subject receives the total 7 days of treatment per cycle. If the azacitidine dose interruption is >3 days, discuss with the Medical Monitor.

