- Concomitant medications review
- Transfusion log

#### 6.5.5 Day 15

- Physical examination
- Weight
- ECOG performance status ([Appendix II](#))
- Vital signs, including blood pressure, heart rate, respiration rate and temperature
- Hematology, including complete blood count with white blood cell differential
- Serum chemistry, including sodium, potassium, chloride, magnesium, CO2, BUN, creatinine, glucose, calcium, albumin, total protein, total bilirubin, AST, ALT, alkaline phosphatase
- Creatinine clearance (Cockcroft-Gault method; [Appendix I](#))
- Ophthalmologic evaluation, per [Table 16](#)
- Clinical safety assessment
- Concomitant medications review
- Transfusion log

#### 6.5.6 Day 22

- Physical examination
- Weight
- ECOG performance status ([Appendix II](#))
- Vital signs, including blood pressure, heart rate, respiration rate and temperature
- Clinical safety assessment
- Concomitant medications review

- Transfusion log

## 6.6 Cycle 2

### 6.6.1 Day 1

- Physical examination
- Weight
- ECOG performance status ([Appendix II](#))
- Vital signs, including blood pressure, heart rate, respiration rate and temperature
- Hematology, including complete blood count with white blood cell differential
- Serum chemistry, including sodium, potassium, chloride, magnesium, CO2, BUN, creatinine, glucose, calcium, albumin, total protein, total bilirubin, AST, ALT, alkaline phosphatase
- Creatinine clearance (Cockcroft-Gault method; [Appendix I](#))
- Coagulation profile
- APR-548 administration. Cycle 1 Day 1 treatment may proceed following ophthalmologic evaluation performed by retina specialist to ensure there are no clinically significant ocular-associated AE
- Azacitidine administration on Days 1-7. Azacitidine is administered 1 hour ( $\pm$ 15 min) after APR-548
- Blood sampling for APR-548 and azacitidine PK, per [Table 13](#)
- ECG: standard 12-lead ECG with subject in a semi-recumbent position, per [Table 15](#)
- Serum or urine  $\beta$ hCG for female subjects of childbearing potential
- Ophthalmologic evaluation, per [Table 16](#)
- Clinical safety assessment
- Concomitant medications review
- Transfusion log

### 6.6.2 Days 2 - 7

- Vital signs, including blood pressure, heart rate, respiration rate and temperature
- APR-548 administration on Days 2-4
- Azacitidine administration on Days 2-7. On the days of concomitant administration, azacitidine is administered 1 hour ( $\pm$ 15 min) after APR-548

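### Table 13 takes no azacitidine plasma at 1.5 h, the nominal azacitidine peak, so the Cmax planned in Section 8.7 will read low and Tmax late (minor)

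*Combined protocol and SAP*

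**What the plan says.** **Dosing clock.** Section 4.3.2: "On the days of concomitant APR-548 administration, azacitidine will be administered 1 hour" (±15 min) after APR-548. Section 5.1.2 agrees: "On days of concomitant APR-548 intake, azacitidine should be administered 1 hour" (±15 min) after it.

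**Azacitidine kinetics.** Section 2.4 gives a half-life of 41 ± 8 minutes and says that Cmax "is reached after about 30 minutes".

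**Sampling.** Section 7.3: "Plasma samples from Cycle 1 for analysis of azacitidine will be taken as indicated in" Table 13. Footnote d reads "Plasma samples for azacitidine administration to be taken at the same time as whole blood samples for APR-548". On Cycle 1 Days 1 and 4 it is attached to the 1, 2, 4, 6 and 8 h cells. Footnote c places the 1 h sample directly before azacitidine. The 1.5 h cell on both rows is marked for APR-548 only. Days 2 and 5 have a pre-dose azacitidine sample and nothing more. A note below the table adds: "The PK sampling timepoints (0.25, 0.75, 1.5 hours post dose) can be reduced once the" Cmax and half-life are established.

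**Analysis.** Section 8.7 lists Cmax, Tmax, half-life, AUC, CL/F and Vd/F for azacitidine by non-compartmental methods; the synopsis qualifies that list as applying where appropriate.

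**Interaction aim.** Objective 3 (synopsis and Section 3.2) is the PK interaction between the two drugs. Section 2.4 considers APR-548 as perpetrator unlikely, "but the drug-drug interaction will be investigated as part of the current trial". The only with/without PK endpoint (Section 8.3.2, item 10) concerns APR-548.

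**Later cycles.** The Day 1 lists in Sections 6.6.1 (Cycle 2) and 6.7.1 (Cycle 3 onwards) carry the same line as Cycle 1, "Blood sampling for APR-548 and azacitidine PK, per" Table 13. Table 13 marks no azacitidine sample after Cycle 1, and Table 12, Section 7.3, Section 8.7 and the synopsis keep azacitidine sampling in Cycle 1.

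**The concern.** The one draw that coincides with the expected azacitidine peak is taken for APR-548 but not assayed for azacitidine. The next azacitidine sample nominally comes half an hour after the peak, and the one after that at 3 h post-dose, or 180/41 = 4.4 half-lives. A single sample therefore carries nearly all the information on Cmax and Tmax, and it is nominally on the falling limb. Observed Tmax cannot nominally be earlier than 1 h, against about 0.5 h in Section 2.4.

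At stake is the descriptive azacitidine PK in Section 8.7 and how objective 3 will be read. Azacitidine PK is not a listed endpoint, and no escalation, RP2D or stopping rule refers to it.

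**Working it through.** The plan states no figure to reproduce. The profile shapes below are assumptions, because Section 2.4 gives only Cmax at about 30 min and a half-life of 41 ± 8 min (33–49 min used).

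**1. Clock.**
- Nominal peak: 1 h + 0.5 h = 1.5 h after APR-548.
- First post-azacitidine sample: 2 h − 1 h = 1 h after azacitidine.
- With both ±15 min windows, azacitidine falls at 0.75–1.25 h and the 2 h draw at 1.75–2.25 h, so that sample is 30–90 min after azacitidine.
- A 1.5 h draw (1.25–1.75 h) would be 0–60 min after azacitidine.

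**2. Simple decline from a 30-min peak.** Share at 1 h = exp(−ke × 0.5), with ke = ln 2 / half-life. At 41 min, ke = 0.6931/0.6833 = 1.014 per h, giving 0.602. At 33 and 49 min: 0.533 and 0.654.

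**3. One-compartment s.c. model.** C(t) is proportional to exp(−ke·t) − exp(−ka·t), with ka solving ln(ka/ke)/(ka − ke) = Tmax. For Tmax 0.5 h and half-life 41 min, ka = 3.480 per h. Ranges are over half-life 33–49 min.

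| Assumed Tmax | Share of peak at 1 h (as planned) | Share of peak at 0.5 h (1.5 h draw) |
|---|---|---|
| 20 min | 0.544–0.642 | 0.929–0.943 |
| 30 min | 0.757–0.797 | 1.000 |
| 40 min | 0.911–0.920 | 0.963–0.966 |

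**4. I.v. infusion.** The duration is not stated. Assuming 10–40 min, the 1 h sample is at 0.35–0.75 of peak and a 0.5 h sample at 0.66–0.87.

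**5. Windows.** Simulated chance that the highest observed value is below 90% of true Cmax (s.c. model, half-life 41 min, dosing and draw errors uniform within ±15 min):
- Tmax 20 min: 99% as planned, 46% with the 1.5 h sample.
- Tmax 30 min: 83% and 19%.
- Tmax 40 min: 43% and 7%.

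**6. AUC to 7 h after azacitidine, linear trapezoid.** Times are {0, 1, 3, 5, 7} h as planned, then with 0.5 h added.
- S.c. model, Tmax 30 min, half-life 41 min, in units of Cmax. As planned: 0.389 + 0.889 + 0.126 + 0.017 = 1.421. With 0.5 h: 0.250 + 0.444 + 0.889 + 0.126 + 0.017 = 1.727. Here Cmax = 0.602 when the true AUC is 1/ke, so multiplying by 0.602 × 1.014 gives 0.868 and 1.055 of true.
- Linear rise to 30 min then simple decline, half-life 41 min. True area: 0.25 + 1/1.014 = 1.236. As planned: 1.084/1.236 = 0.877. With 0.5 h: 1.433/1.236 = 1.160. Over 33–49 min: 0.85–0.89 as planned and 1.12–1.21 with 0.5 h.

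The error shrinks in the first shape and grows in the second.

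**7. Azacitidine without APR-548.** Both post-dose profiles (Days 1 and 4) fall on days when APR-548 is given. Azacitidine alone is given on Days 5–7, where the only sample is the Day 5 pre-dose one. Azacitidine profiles without APR-548: none.

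**The case against.** **The mark may be absent on purpose, or lost.** From 1 h onward, 1.5 h is the only time without footnote d and also the only one that may later be dropped, so the omission may be deliberate; the text gives no reason. A superscript could also have been lost in reading the table, although the same gap on both rows makes that unlikely. The sponsor should check its source table. In either case Section 8.7 still plans Cmax and Tmax from a schedule without the nominal peak.

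**The size depends on the model.** This stands. A reader might take the 83% to 19% result as the size of the effect, but it is one point in a range from 99% to 46% down to 43% to 7%. A reader might also infer that the extra sample improves AUC. The linear rule does not support that (step 6), and the protocol names no AUC rule.

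**The draw is not free.** This also stands. Protecting 1.5 h from the reduction keeps draws that later subjects could have been spared.

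**The interaction is not wholly unexamined.** It is tempting to conclude that the trial can say nothing about APR-548's effect on azacitidine. That goes too far. Azacitidine is profiled across APR-548 dose levels, and Day 1 against Day 4 compares single with repeated APR-548 within subjects. Both comparisons are weak, and neither is a with/without contrast.

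**The visit lists are editorial.** Agreed. Both lines defer to Table 13, so it is speculation that sites would draw extra samples.

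**Conclusion.** The point holds as a minor one. With the schedule as marked, azacitidine Cmax is biased low and Tmax late. At nominal times the first post-dose sample is at 54–92% of peak for s.c. dosing (one-compartment, Tmax 20–40 min, half-life 33–49 min), or 53–65% by simple decline. The direction follows from the protocol's own clock and kinetics; the size rests on assumed profiles. Only the Cmax and Tmax gain from a 1.5 h sample is established.

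A reader might infer a threat to dose finding. The documents do not support that, because the exposure limits and escalation rules concern APR-548.

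Secondary: the trial has no direct within-trial with/without contrast for APR-548's effect on azacitidine, and objective 3 and Section 2.4 do not say so. Editorial: Sections 6.6.1 and 6.7.1 conflict with Tables 12 and 13, Sections 7.3 and 8.7, and the synopsis.

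**What to change.** 1. **Table 13.** Add footnote d at 1.5 h on Cycle 1 Days 1 and 4, and exempt that draw from the optional reduction while azacitidine PK is collected. In Section 8.7, state that azacitidine parameters use actual times after azacitidine dosing. If the sample is not wanted, report azacitidine Cmax, Tmax and AUC as limited by sparse early sampling.
2. **Objective 3 (synopsis and Section 3.2) and Section 2.4.** State that there is no azacitidine profile without APR-548, so APR-548's effect on azacitidine can be examined only through the weak across-dose and Day 1 versus Day 4 comparisons.
3. **Sections 6.6.1 and 6.7.1.** Remove azacitidine from the PK sampling lines.

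**Cost.** At most 2 × 46 = 92 extra plasma samples and assays. They use an existing draw until the reduction is invoked; after that, each subject keeps two 1.5 h draws that could have been dropped. Because of the ±15 min windows the peak is still not guaranteed. Items 2 and 3 are wording only. All three fit in one amendment, which needs IRB/IEC approval under Section 10.2, with a matching laboratory manual update.

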**Table 14. PK blood sampling timepoints for MQ-H2O, MQ-Cys and MQ-GSH for subjects at selected centers**

Period	Day	Time relative to APR-548 dose (h)									
		Pre-dose	0.25 a	0.5 a	0.75 a	1 b	1.5 b	2 b	4 b	6 b	8 b
Safety Run-In (APR-548 monotherapy)	4	×	×	×	×	×	×	×	×	×	×
	5	×									
Cycle 1 (APR-548 + Azacitidine)	4	×	×	×	×	×	×	×	×	×	×
	5	×									

a. A window of  $\pm 5$  minutes is allowable for this collection.

b. A window of  $\pm 15$  minutes is allowable for this collection.

The PK sampling timepoints (0.25, 0.75, 1.5 hours post dose) can be reduced once the  $C_{max}$  and  $T_{1/2}$  are established. The Sponsor will provide a written memo to sites, which should be submitted to IRBs and can be implemented per local site requirements.

## 7.4 Pharmacodynamics

Blood samples for PD biomarkers are collected pre-dose, 8 hours post dose, and 24 hours post dose on Day 1 and Day 4 in safety run-in and Cycle 1 (the 24 h post-dose timepoints correspond to pre-dose Day 2 and Day 5, respectively). Flow cytometry analysis will be completed by central laboratory.

Peripheral blood/bone marrow (whichever sample is collected for disease response assessment) mononuclear cells collection for exploratory biomarker sample testing, including DNA mutation panel, RNA expression profile, *TP53* VAF by NGS, will be done at each response assessment. Descriptive statistics will be written. Not all listed analyses may be performed.

## 7.5 Electrocardiographic Assessment

[Table 15](#) describes the routine ECG requirements.

**Table 15. ECG assessment requirements**

Time Point	ECG, number	Timing
Screening	TriPLICATE	Within 28 days of study treatment
Safety Run-In, Day 1	TriPLICATE	Pre-dose; 0.5, 1, 2, 3 and 4 hours after APR-548 administration ( $\pm 10$ min)
Safety Run-In, Day 2	TriPLICATE	Pre-dose
Safety Run-In, Day 4	TriPLICATE	Pre-dose; 0.5, 1, 2, 3 and 4 hours after APR-548 administration ( $\pm 10$ min)
Safety Run-In, Day 5	TriPLICATE	Pre-dose
Cycle 1, Day 1	TriPLICATE	Pre-dose; 0.5, 1, 2, 3 and 4 hours after APR-548 administration ( $\pm 10$ min)
Cycle 1, Day 2	TriPLICATE	Pre-dose
Cycle 1, Day 4	TriPLICATE	Pre-dose; 0.5, 1, 2, 3 and 4 hours after APR-548 administration ( $\pm 10$ min)
Cycle 1, Day 5	TriPLICATE	Pre-dose
Cycles 2+, Day 1	TriPLICATE	Pre-dose, 1- and 2-hours post dose ( $\pm 10$ min)
End of Treatment	TriPLICATE	-

Schedule of ECG assessments may be modified upon Sponsor notification, based on available data.

The following ECG parameters are to be captured in eCRF: heart rate, PR interval, RR interval, QT interval and QT interval corrected for heart rate using Fridericia's formula:  $QTc = QT/RR^{1/3}$ .

If a subject starts treatment with a medication known to prolong QT interval at any time during the study treatment period, an additional pre- and post-dose (4 hours after APR-548 administration,  $\pm 10$  min) ECG should be performed on the next APR-548 treatment day unless such pre- and post-dose ECGs are already required on that next APR-548 treatment day per the schedule of study assessments.

## 7.6 Ophthalmological Evaluation

[Table 16](#) describes the schedule of ophthalmological evaluation.

**Table 16. Ophthalmological evaluation**

Assessments a	Screen-ing b, c	Safety Run-In d		Cycle 1 (1 st combination cycle)	Cycle 2 & 3		Subse- quent Cycles	End of treatm ent i
		D15 e	D28 e		D1 f	D15 f		
Complete ophthalmic exam b	×	×	×	×	×	×	×	×
Visual field test g	×	×		×	×	×	×	×
SD-OCT h	×	×	×	×	×	×	×	×
Color fundus photography	×	×	×	×	×	×	×	×
Fundus autofluorescence	×	×		×	×	×	×	×
Fluorescein angiography	×			×	×	×		

- a. All evaluations are to be performed prior to administration of a next scheduled dose.
- b. Complete ophthalmic exam includes best corrected distance visual acuity utilizing Early Treatment Diabetic Retinopathy Study (ETDRS) scale, intraocular pressure measurement using Tono-Pen or Goldmann (the same modality should be used throughout the study), slit lamp exam (anterior and posterior segments), dilated fundus (using indirect ophthalmoscopy). Additional testing may be performed at discretion of the retina specialist. Applicable ophthalmologic assessment may be repeated at an unscheduled visit during the study if clinically indicated. An ophthalmic CRF is completed by the examining retina specialist at each visit.
- c. Performed within 14 days of initial APR-548 administration.
- d. Applies to the 28-day safety run-in period for APR-548 monotherapy and the 28-day safety run-in period for APR-548 in combination with azacitidine.
- e. A window of  $\pm 4$  days is allowable for this visit. This visit has to be completed prior to Cycle 1 Day 1 (1st combination cycle).
- f. A window of  $\pm 5$  days is allowable for this visit.
- g. An automated, threshold perimetry with Humphrey visual field analyzer using 30-2 testing protocol.
- h. Spectral domain optical coherence tomography of the macula and optic nerve, including ganglion cell complex analysis with study-specified and standard data acquisition algorithms utilized.
- i. Visit conducted at 28 days ( $\pm 14$  days) after study treatment discontinuation.

Please consult the A20-11202 study ophthalmic reference manual and ocular assessment worksheets for details. Ocular assessment worksheets are to be completed by retina specialist and submitted to the site for each visit.

## 8.0 STATISTICS

Demographic data and disease-related characteristics will be summarized using descriptive statistics (count and percent, mean, median, standard deviation, minimum, maximum). Continuous variables will be presented by *n*, mean, median, standard deviation and range (minimum and maximum), and categorical variables will be presented by count and percentage of subjects as appropriate. Data will be presented by each dose level in safety lead-in dose-finding portion and in the expansion portion. All subject data, efficacy and safety data will be summarized.

## 8.1 Sample Size

This trial assumes a sample size of up to 46.

## 8.2 Analysis Populations

Safety population: Subjects will be evaluable for safety if they receive at least one dose of APR-548. The safety population will be the primary analysis population used for all analyses such as subject disposition, subject demographics, exposure, safety parameters and efficacy parameters. The safety population will be the primary analysis population for efficacy.

EE population: All subjects who complete at least one treatment cycle of APR-548 and who have at least one post-treatment clinical response assessment. The EE population will be the secondary analysis population for efficacy.

PK population: Subjects will be evaluable for PK if at least one sample for PK evaluation has been obtained.

## 8.3 Endpoints

### 8.3.1 Primary

1. Occurrence of DLTs, classified and graded according to the NCI-CTCAE version 5.0
2. Frequency of TEAEs and SAEs related to APR-548 alone and in combination with azacitidine
3. RP2D of APR-548

### 8.3.2 Secondary

1. Rate of CR
2. DOCR, defined as the time from documentation of CR to disease relapse
3. DOR, defined as the time from documentation of tumor response to disease relapse/progression or death as a result of any cause
4. ORR is the proportion of subjects achieving HI, PR, CR, marrow CR by modified IWG 2006 criteria
5. Rate of and time to AML transformation, according to WHO criteria
6. OS

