#### **4.1.1 Treatment Duration**

Subjects may continue treatment with APR-548 and azacitidine until disease progression, development of other unacceptable toxicity, confirmed pregnancy, HSCT, death, withdrawal of consent, or study termination, whichever occurs first. Subjects who experience disease progression per the applicable response criteria who are, in the opinion of the investigator, benefiting from treatment, may be allowed to continue on study drug with approval of the Medical Monitor.

Following discontinuation of study drug, subjects are to attend a follow-up visit 28 days after the last dose of study drug for final assessments. When study drug is withheld from a subject in order to resolve a toxicity and the subject does not subsequently restart treatment, end of treatment is defined as the date when the study drug was first held. Subjects should proceed with end of treatment assessments, safety, and survival follow-up. If the decision to not restart study treatment comes outside of the 28-day safety follow-up window, the subject should have an End of Treatment visit and proceed with survival follow-up.

Subjects who achieve an adequate response to treatment with APR-548 and meet other criteria required to undergo HSCT may proceed to HSCT after discontinuation of APR-548. If a subject proceeds to HSCT, evaluation of the extent of disease, response to treatment, and any new antineoplastic therapies will be collected at least monthly as long as the subject remains in remission and assessed as part of the study until relapse, death, withdrawal of

consent, loss to follow-up, or end of study, whichever comes first. If a subject discontinues APR-548 to undergo HSCT, but is then deemed ineligible for HSCT, the subject may restart APR-548 with Medical Monitor approval.

All subjects that enter survival follow-up will be contacted every two months for assessment of survival status and new antineoplastic therapies. Please see Section [6.9](#) for details on long-term follow-up.

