## 8.6 Efficacy

CR rate will be summarized for the safety and EE subjects as the proportion (%) of subjects with CR. In addition to presenting the CR rate, its associated exact 95% CI for each treatment arm will also be presented.

DOR is defined as the time from the date when criteria for response are met to the date of PD or death due to any cause, whichever occurs first. Subjects alive with no PD will have their DOR censored at the date of the last clinical assessment. The DOOR will be summarized in each treatment arm by providing the median DOR together with associated 95% CI, using Kaplan-Meier methodology.

Overall response will be summarized in number (%) of subjects in each category of responses (CR, PR, mCR with HI, mCR without HI, HI). ORR will be analyzed by using the similar method as primary endpoint CR. DOR, as defined above, will also be evaluated in regard to ORR. Time to AML is calculated from first day of study treatment to first onset of AML. Kaplan-Meier methodology will be utilized. Rate of AML transformation will be analyzed by using the similar method as primary endpoint CR.

Survival data are collected at treatment and follow-up periods. Subjects will be followed until death or withdrawal of consent from the study, whichever occurs first.

OS is defined as the number of days from the first day of treatment to the date of death due to any cause. Kaplan-Meier methodology will be utilized.

RFS is defined as the time from the date of randomization to disease relapse or death, whichever occurs first. If neither event occurs, RFS will be censored at the date of the last clinical assessment. Kaplan-Meier methodology will be utilized.

Time to AML, OS and RFS will be analyzed using the similar methods as DOR.

Transition rate to HSCT will be analyzed using the similar methods as CR.

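### Duration of CR is defined to end at relapse only, while DOR and RFS count death, and the plan gives no clear rule for a death in remission

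*Combined protocol and SAP*

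**What the plan says.** The endpoint lists in the synopsis and in Section 8.3.2 define the second secondary endpoint as "DOCR, defined as the time from documentation of CR to disease relapse". The third item in the same lists is "DOR, defined as the time from documentation of tumor response to disease relapse/progression or death as a result of any cause". Section 3.2 lists duration of CR and duration of overall response as separate objectives, so each should yield its own figure.

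The analysis text has no paragraph on DOCR by that name. Section 8.6 ends DOR at the earlier of PD and death from any cause, and adds "Subjects alive with no PD will have their DOR censored at the date of the last clinical assessment". It continues: "The DOOR will be summarized in each treatment arm by providing the median DOR together with associated 95% CI, using Kaplan-Meier methodology". The paragraph on overall response then says "DOR, as defined above, will also be evaluated in regard to ORR". Section 7.2.2 and the synopsis carry nearly the same duration text; the synopsis adds relapse to PD. DOOR is not in the list of abbreviations, whereas DOCR and DOR both are.

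RFS, in the synopsis and Sections 7.2.5 and 8.6, ends at relapse or death.

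**The concern.** Read literally, a subject in CR who dies without relapse has a DOR event and an RFS event on the day of death, but no DOCR event. The definition does not say what happens to that subject in the DOCR analysis. If the death is censored under Kaplan-Meier, the estimate treats the subject as someone who could still have relapsed later. The median can then only stay the same or rise.

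Such deaths are plausible here. Section 2.2 puts median survival in TP53-mutant disease at 5 to 9 months. Section 5.3.4 warns of infection with a fatal outcome during neutropenia. Section 4.1.1 lets responders who meet transplant criteria leave treatment for transplant (they "may proceed to HSCT after discontinuation of APR-548") and follows them until relapse or death, so deaths in remission would be observed.

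At stake is the meaning of one reported figure. CR duration could look longer than response duration because of the event definition alone. The trial is also open-label, and if the rule stays open, the handling of deaths could be settled after the data are known.

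**Working it through.** **Step 1. Compare the definitions.**

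| Endpoint | Where | Ends at | Death an event? |
|---|---|---|---|
| DOCR | Synopsis endpoints, 8.3.2 | relapse | not named |
| DOR | Synopsis endpoints, 8.3.2 | relapse, progression or death | yes |
| DOR | Synopsis efficacy analyses | relapse, PD or death | yes |
| DOR | 7.2.2, 8.6 | PD or death | yes |
| RFS | Synopsis efficacy analyses, 7.2.5, 8.6 | relapse or death | yes |

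DOCR is the only one of these durations that omits death. The stated duration censoring rule applies to subjects who are alive without PD (relapse or PD in the synopsis), so it says nothing about a subject who has died.

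**Step 2. Read DOOR both ways.** If it means DOR, then DOCR has a definition that omits death and no analysis or censoring rule of its own. If it means DOCR, the analysis text counts death and the endpoint lists do not. On this second reading, Sections 7.2.2 and 8.6 also name PD where the endpoint lists name relapse, and Appendix V gives those two different criteria.

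**Step 3. Size, if deaths in remission are censored.** The plan states no DOCR median, CR rate or rate of death in remission, so there is no figure to reproduce and every input here is assumed. Let the relapse hazard λr and the hazard of death in remission λd be constant, with f = λd/(λr + λd).

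- Median with deaths censored: ln 2/λr.
- Median with death as an event: ln 2/(λr + λd).
- Ratio: (λr + λd)/λr = 1/(1 − f).

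For illustration take a relapse-only median of 8 months. The relapse-or-death median is then 8 × (1 − f).

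| f (assumed) | Relapse-or-death median, months | Relapse-only median is larger by |
|---|---|---|
| 0 | 8.0 | 0% |
| 10% | 7.2 | 8/7.2 − 1 = 11% |
| 20% | 6.4 | 8/6.4 − 1 = 25% |
| 33% | 5.4 (5.36) | 8/5.36 − 1 = 49% |

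The percentages depend only on f, not on the 8 months.

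**Step 4. Check the direction in small samples.** A simulation assumed 10 or 20 subjects in CR, a true relapse-or-death median of 8 months (a different use of 8 from Step 3), uniform censoring between 6 and 24 months, and f from 10% to 40%, with 4,000 runs per setting. The deaths-censored median was never below the median with death counted. At f = 20% the typical estimates were 7.02 against 9.59 months with 10 CRs, and 7.55 against 10.08 months with 20. With 10 CRs the median was not reached in 2.9% of runs with death counted and in 12.8% with deaths censored.

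**The case against.** The strongest reply is that the documents never say deaths in remission are censored. The only Kaplan-Meier duration analysis they specify counts death, and its censoring rule covers living subjects. DOOR may be a slip for DOCR, and the word also in "DOR, as defined above, will also be evaluated in regard to ORR" suggests that the preceding, death-inclusive paragraph was meant for CR duration. On that reading the analysis is already sound. This part stands: a reader might infer that median DOCR is overstated under the plan as written, and the documents do not support that as a fact. They do not remove the problem either. On that reading the endpoint definition contradicts the analysis, and on the other reading DOCR omits death and has no rule.

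Two further inferences should be resisted. The plan permits transplant in responders; it does not push them towards it. And 11% to 49% is not an estimate for this trial: f is assumed, and the 8 months in Section 2.2 is median overall survival, not CR duration. CRs may also be few. If the CR rate were the 10% that Section 2.4 reports from the azacitidine reanalysis (an assumption for this trial), 46 subjects would give 0.10 × 46 = 4.6, about 5 CRs, and one death could move the median erratically or leave it unreached.

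It is also true that time to relapse is a legitimate quantity when death is handled explicitly, and that DOR, RFS and OS make these deaths visible elsewhere.

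**Conclusion.** The point holds as an inconsistency with a conditional bias. DOCR ends at relapse only in both endpoint lists, against a death-inclusive DOR in the same lists, a death-inclusive RFS, and a death-inclusive duration analysis attached to an undefined term. If the definition is applied with Kaplan-Meier and deaths in remission are censored, median DOCR is biased upward whenever such deaths occur before the median. The factor is 1/(1 − f) under constant hazards: 11% to 49% for an assumed f of 10% to 33%, and nothing if no such deaths occur. The direction is secure; the size cannot be derived from the documents.

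The consequence is limited. DOCR is a descriptive secondary endpoint. No test or sample size depends on it, and the RP2D is set from mBED, exposure and DLTs. The correction is still worth making, because it is short and both readings of DOOR call for the same edit.

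**What to change.** - In the synopsis endpoints and Section 8.3.2, define DOCR as the time from first documentation of CR to relapse or death from any cause, whichever occurs first.
- In the synopsis efficacy analyses and Sections 7.2.2 and 8.6, replace DOOR with the intended term or terms, and state that subjects alive in CR are censored at the last clinical assessment. Changing the endpoint lists alone would leave DOOR undefined and DOCR without a censoring rule.
- If a relapse-only view is wanted, report cumulative incidence of relapse with death as a competing event, under its own name.

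The cost is a few phrases and a slightly shorter reported CR duration if deaths in remission occur. Relapse and death are already collected, so no extra data are needed.
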